D5. Intervention to be Tested. A detailed description of the intervention to be tested can be found in Clin-Trls Section 4, Narrative Study Description and Interventions. Briefly, children in the study will be randomly identified to take part in the Voucher Program. During the summer, children in the Voucher Program will receive a voucher that covers enrollment fees associated with accessing a day camp operated at a park near their school. The total value of the voucher for a single child for an 8-week summer will be \$880 (\$110 per week). This fee covers all operating expenses plus transportation to and from the camp. The summer day camps (defined in **Section A5**) will be existing summer day camps operated by the Recreation Commission. The summer day camps provide indoor and outdoor opportunities for children to be physically active each day, provide enrichment and academic programming, as well as breakfast, lunch, and snacks. Importantly, these camps are enrolled in the USDA Summer Food Service Program. Thus, all meals adhere to the Summer Food Service Program nutrition guidelines. The camps employ 1 staff member for every 12 children and operate daily (Mon-Fri) for the entire summer. The camps open at 7am and close at 6 pm daily. Physical activity opportunities are scheduled for 3 to 4 hours each day, with the remaining 4 to 5 hours dedicated to enrichment or meals/snacks. These camps will operate according to routine practice, with no outside assistance from the investigative team. Children randomly assigned to the control group will be enrolled in the same schools as those randomized to receive the Voucher Program. The comparison/control group will not receive a voucher to attend a summer camp. It is possible that children serving in the control/comparison condition may elect to voluntarily participate in a summer program. However, based on enrollment numbers from pilot work (see **Section C**), the limited number of weeks children were enrolled (avg. of 2 weeks), the associated costs of enrolling (i.e., \$880 per child), and national data indicating that few children from low-income families attend summer day camps (see **Section A5**), it is unlikely that comparison/control children will enroll in a summer day camp. Thus, there is a high degree of confidence that the comparison/control group will represent weight and fitness outcomes associated with children not attending a summer program.

[figure not shown]

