Figure D6. Schedule of school year and summer measurements

Abbreviations—body mass index (BMI), cardiorespiratory fitness (CRF)

D6. Primary and Secondary Measures. Details for implementation of the measurement plan will be finalized in consultation with the CTL Core with respect to training of data collectors, record-keeping procedures, data capture procedures, and construct scoring. For a detailed description of the primary, secondary, covariate, predictor, and determinant measures see Clin-Trls Section 4, Narrative Study Description and Outcome Measures. All measures were selected in consultation with our consultants, the participating school district, and the Recreation Commission. The measures selected 1) represent state-of-the-art techniques that are known to produce valid and reliable data and 2) minimize burden on the participating families.

D6.1. Primary Outcomes (Specific Aim 1). All students enrolled in the study will take part in a cardiovascular fitness (CRF) test (i.e., PACER)[2-8] and have their height and weight measured by trained research staff using standard procedures during a regularly scheduled physical education class. This information will be used to compare changes in BMI (translated into age-sex z-scores [zBMI]) and CRF during summer and the school year. The tests are valid and reliable and used extensively with the proposed age groups.[59-63] Peak height velocity will also be collected as a marker of biological maturation (covariate in statistical models).[1]

D6.2. Secondary Outcomes (Specific Aim 2). Briefly, physical activity, sedentary behaviors, and sleep will be collected using a non-dominant wrist-placed ActiGraph Link for 9-days (common timeframe to collect physical

activity data).[45, 64-74] Children's screen time will be assessed using a parent-proxy report measure completed daily for 9 days by the parent with their child. Parents/children will estimate the total amount of time (hours and minutes) spent in front of a screen that day (e.g., TV, computer, video-game, smartphone, and tablet). [75] Dietary behavior of participants will be estimated using several dietary screeners that have been found to be valid and reliable when compared to multiple pass dietary recall.[76-90]

Table D6. Description of Measures for Primary and Secondary Outcomes and Exploratory Variables at the Child Level

Outcome	Construct	Assessment/Tool	Description/Protocol

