D7. Protocol for School and Summer Data Collection. This section describes the protocols for administering the FITNESSGRAM assessments, both H&W and PACER, over a 9-day period during the school year and summer. During the school year children will run the PACER and have their H&W collected during physical education class prior to and following each summer. During this class children will also be provided the activity monitors (ActiGraph), and surveys to take home to their parent for completion. For summer, H&W and PACER will not be collected (see Figure D6.) but monitors and surveys will be distributed during scheduled family days at the child's elementary school (see below for details). During summer and the school year, the parent/guardian will receive text prompts with daily reminders to complete the survey instruments during the 9-day assessment. For the summer, parents/guardians and their child will be contacted in one of two ways. The first primary contact will be through a day-long (8am-5pm) open house at their child's school. Parents/guardians of children participating in the study will be texted two weeks and one week prior about attending a Saturday open house. Parents/guardians showing up to the in-person summer open house will receive \$50 when returning the devices and completed survey packet.

D8. Power Considerations, Statistical Design, and Missing Data. The SDM Core assisted the PI with respect to the analytic plan described in this application. The SDM Core will assist the research team with the codebook (for raw data and constructs), specification of missing data flagging and procedures, data entry/capture, data management, preliminary examination of distributions in preparation for analyses, conduct of statistical analyses, and assistance in interpretation of programming output. All analyses will be completed by the SDM Core, which will have individuals with extensive expertise in the statistical models required for

analyzing the data collected in the proposed project.

D8.1. Power Considerations. Details of the power analysis completed for this study are presented in Clin-Trls Section 4, Statistical Power and Design. Based on the hypothesized difference between z-BMI change for children who receive and do not receive a voucher (i.e., 0.22 vs. 0.11) this study is sufficiently powered.

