D8.4. Missing Data. Across this study, four scenarios with missing data are possible: 1) missing items within children; 2) missing cases (i.e., children not present to complete assessments); and whether the missingness is for 3) missing determinants/covariates or 4) missing outcomes (e.g., zBMI, physical activity). For missing assessments, such as incomplete diaries, parent surveys, accelerometer data, or BMI, the parents will be contacted and, where willing, they will be invited to re-complete the missing assessments. Where children are not present at the school on days of BMI assessments or to pick-up their monitor and surveys, data collectors will return to the camp on another day to complete the assessments. For any assessments not obtained, models will be estimated using full information maximum likelihood estimators, as well as employ multiple imputation techniques. These two strategies for handling missing outcome data will be compared (analogous to a sensitivity analysis) to determine the most appropriate way to handle the missingness. Based on previous large-scale group randomized trials,[102, 131] full information maximum likelihood estimators provide a robust and unbiased estimate. This is consistent with literature comparing this estimator to models using multiple imputation.[132] For missing determinant/covariates that are continuous, multiple imputations will be employed. For missing determinant/covariates that are categorical, a missing dummy variable technique will be used rather than imputing categorical data.[133, 134]

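### SAP D8.4 sends make-up visits for children missed at school to the camp, where the protocol takes no BMI and few control children are expected

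*SAP*

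**What the plan says.** SAP D8.4 gives two ways to recover a missed assessment before any modelling.

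- **Parent contact.** For incomplete diaries, surveys, "accelerometer data, or BMI, the parents will be contacted and, where willing, they will be invited to re-complete the missing assessments".
- **Staff visit.** The trigger is "Where children are not present at the school on days of BMI assessments or to pick-up their monitor and surveys". The action is that "data collectors will return to the camp on another day to complete the assessments".

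Whatever is still missing goes to full information maximum likelihood (FIML) and multiple imputation.

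The protocol sets the routine collection sites. D6.1 says that enrolled children will "have their height and weight measured by trained research staff using standard procedures during a regularly scheduled physical education class". D7 says that in the school year "children will run the PACER and have their H&W collected during physical education class prior to and following each summer", and that neither measure is taken in summer. For summer, D7 says that "monitors and surveys will be distributed during scheduled family days" at the child's elementary school. It announces two ways of contacting families in summer and describes only the first, a Saturday open house at the school.

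D5 places the camps at parks near the schools, running on weekdays in summer. Control children attend the same schools and receive no voucher, and "it is unlikely that comparison/control children will enroll in a summer day camp".

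**The concern.** The staff visit is triggered by absence at one site and carried out at another. Staff cannot return to a place where the missed assessment was not scheduled.

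Two things are at stake. The first is whether the only staff make-up visit in either document can recover a missed BMI, from which the primary outcome zBMI is computed. The second is whether the visit treats the arms alike. The camp is the intervention site, so a recovery procedure located there makes the chance of retrieving a record depend on allocation. Follow-up in a randomised trial should not do that.

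**Working it through.** The plan states no figure on this point, and no stated sample size, power or alpha depends on it. The main check is a comparison of the texts.

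| Assessment | Routine site and time | Make-up site in D8.4 | Can the staff visit recover it? |
|---|---|---|---|
| Height and weight, before and after summer | School physical education class (D6.1, D7) | Camp | No, read literally |
| Monitors and surveys, school year | Handed out in the same class (D7) | Camp | No, read literally |
| Monitors and surveys, summer | Family days or open house at the school; second contact route not described (D7) | Camp | Yes, but mainly in voucher children |

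**Height and weight.** The camps run in summer. A child missed in class before or after summer could be measured at a camp only during summer, when D7 takes no height or weight. Such a value would not be the pre- or post-summer measurement. PACER is not named in D8.4, but it is run in the same class and the same site question applies to it.

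**Parent contact.** This route names BMI and is open to both arms, so a missed BMI is not without remedy. It names no place and depends on the parent's willingness, and so does not settle where staff should go.

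**Summer monitors and surveys.** D7 does not exclude a camp route. If the camp were the only make-up site, D5 implies that it would find mainly voucher children.

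**Illustration for Aim 2, on assumed inputs.** The documents give 80 children in two arms. Everything else here is assumed: 40 per arm, a share *a* absent, a share *p* of absentees recovered through parents in both arms, and a share *c* of the remainder found at camp.

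- Recovered share of absentees: r = p + (1 − p)c.
- With p = 0.30, voucher c = 0.80 and control c = 0: voucher r = 0.30 + 0.70 × 0.80 = 0.86; control r = 0.30.
- With a = 0.20, children observed: 40 × (0.80 + 0.20 × 0.86) = 38.9 against 40 × (0.80 + 0.20 × 0.30) = 34.4.
- Gap between arms: 40 × a × (1 − p) × (voucher c − control c) = 40 × 0.20 × 0.70 × 0.80 = 4.5 children.
- Range for a from 0.10 to 0.30, p from 0.30 to 0.70, voucher c from 0.50 to 0.80 and control c from 0 to 0.10: from 40 × 0.10 × 0.30 × 0.40 = 0.5 to 40 × 0.30 × 0.70 × 0.80 = 6.7 children.

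Turning a gap in completeness into bias needs one more assumption: how absent children differ.

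- Share of absent-type children among those observed: s = ar / (1 − a + ar). In the case above this is 0.172/0.972 = 0.177 against 0.060/0.860 = 0.070, a difference of 0.107.
- If absent children differ by 0.5 SD in summer only, the group difference shifts by 0.107 × 0.5 = 0.054 SD, and FIML using the spring value removes none of it.
- If the same difference is already present in spring, and the 0.80 correlation from SAP D8.1 applies, the shift is 0.054 × (1 − 0.80) = 0.011 SD.
- Over the ranges above, with absent children differing by 0.25 to 0.75 SD, the shift is 0.003 to 0.117 SD in the summer-only case and 0.001 to 0.023 SD in the stable case.

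The sign follows whichever sign is assumed for the absent children. The 0.80 is an input to the power analysis and is not stated to apply to the Aim 2 measures between spring and summer.

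**The case against.** The strongest objection is that this is a slip. The sentence names the school, 'return' implies going back to where staff had been, and staff could hardly follow the literal text for a school-year BMI. That is probably right, and it makes the practical risk to the primary measure slight. It does not remove the case for correcting the word, because D8.4 is the only text that tells staff where to go.

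Three further objections stand in part. D7 sets no make-up procedure, so D8.4 conflicts with the routine collection site and not with a rival make-up rule. Protocol D6 leaves measurement details to be finalised and refers to a section that is not among these documents, so a fuller procedure may exist. D7's second summer contact route is undescribed, so the contradiction is firm for BMI but not established for summer monitors and surveys.

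A reader might infer three stronger points, and the documents support none of them:

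- *The primary comparison is biased.* The literal BMI rule fails in both arms, parent contact remains open to both, and nothing in the documents shows an effect on Aim 1.
- *Aim 2 is biased in favour of the voucher.* The documents do not say how many children will be absent, how many will be recovered, or how absent children differ.
- *The planned FIML and multiple imputation make the matter negligible.* That also goes beyond the documents. The adjustment helps to the extent that earlier measurements predict the missing ones, and in the summer-only illustration it does not help.

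**Conclusion.** The inconsistency is real, and for BMI it is clear from the text alone. Read literally, the staff make-up visit cannot recover a missed pre- or post-summer height and weight. For summer monitors and surveys the finding is conditional: if the make-up takes place only at camp, Aim 2 completeness could differ by arm, because D5 expects few controls there.

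The size and direction of any bias are not derivable. The illustrated gap of 0.5 to 6.7 children in 40, and the shifts of up to 0.117 SD, rest almost wholly on assumed inputs and concern Aim 2 only. This is a minor point that is worth correcting because the correction is nearly free. Confidence is high for the wording conflict and does not extend to any particular bias.

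**What to change.** 1. In SAP D8.4, for school-year assessments, change 'camp' to 'school' in the make-up sentence. This is a one-word edit: return visits are already planned, and D5 has both arms in the same schools.
2. For summer monitors and surveys, reconcile D8.4 with D7. Describe the second contact route, and state a make-up site and procedure that are equally open to both arms.
3. Report missed and recovered assessments by arm at each time point, so that any imbalance can be seen.

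The cost is slight extra scheduling and staffing for summer make-ups beyond the open house, a short table in the report, and possibly the loss of a few records that would have been easy to retrieve at camp.

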D3. Study Design. The study will be a randomized controlled trial. To distribute costs over years, the study will recruit two cohorts of 1st and 3rd grade students. The first cohort will be recruited in Y01 and the second will be recruited in Y02. Following baseline data collection, children in each cohort will be randomly assigned to either the treatment or control. The sample of students recruited in the 1st grade will be observed during the summer after their 1st grade year and the school year when they are in the 2nd grade. Students recruited from the 3rd grade will be observed in the summer following their 3rd grade year and the school year during 4th grade.

D4. Study Population and Recruitment. Procedures for sampling children are detailed in **Clin-Trls Section 2, Recruitment and Retention Plan**. Briefly, the Recreation Commission operates 11 summer day camps located

at parks. Each camp serves ~100 children every summer. To draw a sample of children, 5 summer camps that operate in the catchment area of elementary schools where $\geq 90\%$ (range = 90%, 100%) of children enrolled are eligible for free and reduced lunch have been identified. A total of 2,333 children (49% female) attend these schools. Children attending the identified schools will be stratified by gender and grade level. In Y01 and Y02, 40 (i.e., 80 total) randomly identified children will be invited to participate in the study.

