Title: Preventing Weight Gain and Unhealthy Behaviors in Children

08/08/2019

D8. Power Considerations, Statistical Design, and Missing Data. The SDM Core assisted the PI with respect to the analytic plan described in this application. The SDM Core will assist the research team with the codebook (for raw data and constructs), specification of missing data flagging and procedures, data entry/capture, data management, preliminary examination of distributions in preparation for analyses, conduct of statistical analyses, and assistance in interpretation of programming output. All analyses will be completed by the SDM Core which will have individuals with extensive expertise in the statistical models required for analyzing the data collected in the proposed project.

D8.1. Power Considerations. The power analysis was performed using G*Power (v.3.1.7) to determine the smallest effect detectable assuming a sample size of 80 participants, power of 0.80, correlation between measures of 0.80, and alpha of 0.05. The study is sufficiently powered to detect a Cohens *d* effect size of 0.20, considered a small effect. Previous large scale longitudinal studies of school year vs. summer weight gain,[12, 14, 36] studies that have provided a structured program to children during the summer,[129, 130] and pilot work have shown that the Cohens *d* effect size of the difference between conditions should be approximately 0.50. Children not receiving the Voucher Program are estimated to experience a mean increase in z-BMI of 0.22 over the summer. Conservatively, children in the Voucher Program are estimated to experience half of the gain in z-BMI during the summer of children not in the Voucher Program (i.e., 0.11 increase in z-BMI). The difference between z-BMI change for children who receive a voucher and do not receive a voucher (i.e., 0.22 vs. 0.11) is equivalent to a Cohens *d* of 0.46. However, the power to detect a small effect was chosen to ensure that the study is able to detect the effect of the primary and secondary outcomes.

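### SAP D8.4 names full maximum likelihood with no small-sample correction; with 80 children the error rate for the arm contrast is about 5.3% to 5.7%, and REML with adjusted degrees of freedom would bring it back to 5%

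*SAP*

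**What the plan says.** SAP D8.4 (Missing Data) states that, for assessments not obtained, "models will be estimated using full information maximum likelihood estimators, as well as employ multiple imputation techniques", and that the two approaches will be compared. It adds that "full information maximum likelihood estimators provide a robust and unbiased estimate". It supports this with experience from earlier large group-randomised trials and with literature comparing the estimator with multiple imputation.

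SAP D8.2 specifies linear and non-linear mixed models for Aims 1 and 2 and structural equation models for mediation. It names no estimator, no degrees-of-freedom method and no reference distribution. Protocol D8.2 is equally silent, so D8.4 is the only estimator instruction in either document.

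The sample is small. SAP D8.1 computes power "assuming a sample size of 80 participants, power of 0.80, correlation between measures of 0.80, and alpha of 0.05", and Protocol D4 says that "40 (i.e., 80 total) randomly identified children will be invited to participate in the study". Protocol D9 randomises individual children to two arms.

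**The concern.** ML estimates variance components as if the mean parameters were known. In a large trial the difference is negligible. With about 40 children per arm it makes standard errors slightly too small, always in the direction of narrower intervals and more false positives.

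REML removes this bias. It uses the same observed outcomes under the same missing-at-random assumption, so the handling of missing outcomes does not depend on choosing ML. Kenward-Roger or Satterthwaite degrees of freedom then replace a normal reference with a suitable t reference.

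At stake is whether the confidence intervals and tests for zBMI and fitness keep the 0.05 error rate assumed in SAP D8.1. Protocol D11 treats retention as a key risk, so some missing follow-up, and hence use of the D8.4 rule, is likely.

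**Working it through.** **Inputs.** 80 children, correlation 0.80, alpha 0.05 and power 0.80 (SAP D8.1); two arms (Protocol D9); height, weight and PACER before and after the summer (Protocol D7). Assumed because the documents do not say: equal allocation (40 per arm), a two-sided test, and a loss of 0%, 20% or 30% (80, 64 or 56 children). School effects are ignored because children are randomised individually.

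**1. The plan's own figure.** SAP D8.1 gives a detectable "effect size of 0.20, considered a small effect". For a two-group, two-occasion interaction test with f = d/2 = 0.10:

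- noncentrality = f² × N × m / (1 − ρ) = 0.01 × 80 × 2 / 0.20 = 8, with 1 and 78 df
- power = 0.798; the smallest d for 80% power is 0.2006

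The figure reproduces. This calculation uses an F test on 78 df, so an analysis based on ML with a normal reference would not match it.

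**2. Size of the ML effect.** For the arm difference in change, two mean parameters are estimated from n changes, so df = n − 2 and

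- SE(ML) / SE(REML) = √((n − 2)/n)
- error, normal reference = 2 × P(t_df > 1.960 × √(df/n))
- error, t reference = 2 × P(t_df > t_0.975,df × √(df/n))

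| Children | SE ratio | ML, t reference | ML, normal reference | REML, normal reference | REML, t reference |
|---|---|---|---|---|---|
| 80 | √(78/80) = 0.987 | 5.29% | 5.66% | 5.36% | 5.00% |
| 64 | √(62/64) = 0.984 | 5.36% | 5.83% | 5.45% | 5.00% |
| 56 | √(54/56) = 0.982 | 5.41% | 5.95% | 5.52% | 5.00% |

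At 80 children the excess under ML with a normal reference is 0.66 points. Of this, 0.29 is present even with a t reference and is due to ML. The other 0.66 − 0.29 = 0.37 comes from the normal reference.

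**3. Simulation check.** 5,000 null data sets per scenario, from a random-intercept model with correlation 0.80, two occasions, sex and age as covariates. Monte Carlo error is about ±0.6 points.

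| Scenario | ML/REML SE ratio | ML, normal reference | REML with Kenward-Roger |
|---|---|---|---|
| Complete data | 0.987 | 5.4% | 4.6% |
| 20% missing follow-up | 0.984 | 5.8% | 5.0% |

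The SE ratios agree with the formula. With complete data the Kenward-Roger method gives 78 df, as expected.

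**4. Cost in precision and power.** Compared with ML and a normal reference, the 95% interval widens by 1.991 / (1.960 × 0.987) = 1.029 at 80 children, that is 2.9%; at 64 it is 3.6% and at 56 it is 4.2%. If the analysts would have used a t reference anyway, the widening at 80 is only 1/0.987 = 1.013, or 1.3%.

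Nominal power, ML with normal reference to REML with t reference:

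- effect of 0.63 SDs of change (80% power with 80 children): 81.5% to 80.0%
- effect of 0.46 SDs of change, 80 children: 55.0% to 52.9%
- effect of 0.46 SDs of change, 64 children: 46.8% to 44.1%

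**The case against.** The strongest reply is that D8.4 is a missing-data section. It weighs all-available-data likelihood against imputation, not ML against REML, and it applies where assessments are not obtained. That is fair. A reader might infer that the plan deliberately rejects REML for the primary analysis, and the documents do not show this. What stands is that the only estimator named is full maximum likelihood and that nothing fills the gap in D8.2.

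Three other stronger readings are tempting and should not be adopted.

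- *The plan's claim of unbiasedness is false.* The sentence concerns the estimate under missing data and makes no claim about standard errors. It also cites comparative literature as well as large trials, and those sources cannot be checked here. The fair comment is only that evidence from large trials does not settle interval coverage with 80 children.
- *The error rate is 6.5% to 7.3%.* Those figures need about seven mean parameters acting on the change contrast, with 80 down to 56 children. SAP D8.2 lists sex and age as covariates with no covariate-by-time terms, so the plan does not support that count.
- *Simulation shows the excess growing with dropout.* A three-wave ML simulation gave 5.9%, 5.4%, 5.9% and 6.2% at 0%, 10%, 15% and 20% dropout per wave, each with error of about ±0.85 points. That is not a demonstrable trend. The formula does imply a rise, but only of about 0.3 points between 80 and 56 children with a normal reference.

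It can also be said that the issue is immaterial in a study that Protocol D12 presents as preliminary evidence for a larger trial. That is largely right and sets the priority of the point, but it is no reason to omit one sentence.

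**Conclusion.** The point holds as a minor improvement. On the plan's 80 children, ML standard errors for the arm difference in change are about 1.3% too small. The true two-sided error is about 5.3% with a t reference or 5.7% with a normal reference, and 5.4% to 6.0% if 56 to 64 children remain. Only a result close to the 0.05 boundary could change.

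These figures assume equal arms, a two-sided test, a two-occasion change contrast with two mean parameters, and the stated losses, which the documents do not give. The plan's primary contrast is the three-way interaction of group, time and setting, so the figures indicate the size of the effect and are not exact for that test. More than half of the excess at 5.7% depends on a normal reference that the SAP never states. That silence leaves an analyst's choice open on the primary test.

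**What to change.** Add to SAP D8.2 and D8.4, and carry into Protocol D8.2: *Linear mixed models for Aims 1 and 2 will be fitted by REML to all observed outcomes, with Kenward-Roger (or Satterthwaite) degrees of freedom. Structural equation models and non-linear mixed models will be fitted by maximum likelihood (full information where data are missing). Multiple imputation will be reported as the planned comparison.* Choose one of the two degrees-of-freedom methods in advance.

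Limit the sentence on robustness and lack of bias in D8.4 to outcome data missing at random.

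The cost is a few lines of text and a software option; no extra data or children are needed. The statistical price is the wider intervals and lower nominal power shown above. The remedy does not correct small-sample error in the non-linear mixed models or the structural equation models, and ML would still be needed if models with different mean structures are compared by likelihood ratio.
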